Table 4: Severity Scale	64
Table 5: Toxicity Grading Scale for Solicited Local Adverse Events.....	64
Table 6: Toxicity Grading Scale for Solicited Systemic Adverse Events.....	65
Table 7: Toxicity Grading Scale for Solicited Other Adverse Events	65
Table 8: FDA Guidance for Grading Clinical Laboratory Abnormalities	66
Table 9: Assessment Criteria.....	69
Table 10: Timeframes for Submitting Serious Adverse Event and Other Event Reports	71

List of Figures

Figure 1: Clinical Trial Design	34
---------------------------------------	----

PROTOCOL AMENDMENTS

Protocol Version	Issue Date
Version 1.0	18 November 2020
Version 2.0	14 December 2020
Version 2.1	16 December 2020
Version 3.0	04 January 2021
Version 3.1	04 February 2021
Version 3.2	18 March 2021
Version 4.0	24 June 2021
Version 4.1	20 July 2021
Version 5.0	10 August 2021
Version 6.0	20 May 2022

Version 6.0 (20 May 2022)

Rationale: A major protocol amendment was made to modify the Phase 1b study design to remove Group G6. Group G6 intended to enroll participants who were not vaccinated with any authorized or experimental COVID-19 vaccine into an open-label arm to receive two doses of VBI-2905a. Due to difficulty enrolling participants who have not been previously vaccinated with an authorized or experimental COVID-19 vaccine in Mexico (the location of the Group G6 study site), Group G6 is being removed from the protocol.

Version 5.0 (10 August 2021)

Rationale: A major protocol amendment was made to modify the Phase 1b study design and make a minor addition to the exclusion criteria in response to the Institutional Ethics and Scientific Committee reviews. The following changes were made:

- Group G7, the placebo arm in the two-dose regimen in participants who were not vaccinated previously, was removed. Text was modified to indicate that in this portion of the study (group G6), VBI-2905a administration will be open label, without a placebo group
- The number of participants in group G5 (placebo recipients) was increased from 9 to 27 to better characterize the kinetics of the longer-term antibody response post-mRNA vaccination and the comparisons with the active group
- The age range of participants in Phase 1b was changed from >18 years of age to 18-54 years of age to be consistent with the Phase 1a part of the study and to minimize the potential impact of age-dependent variability on assessments of immunogenicity.

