8.7.1 Unblinding

Blinding will be guaranteed by the preparation of the study vaccine by an unblinded pharmacist or other qualified study-site personnel with primary responsibility for study vaccine preparation.

Participants will be randomly assigned to groups based on a computer-generated randomization schedule prepared before the study by or under the supervision of the sponsor and using the IWRS.

The investigator will not be provided with randomization codes. The codes will be maintained within the IWRS, which has the functionality to allow the investigator to break the blind for an individual participant.

Data that may potentially unblind the study vaccine assignment (e.g., immunogenicity data, study vaccine accountability data, study vaccine allocation, biomarker, or other specific laboratory data) will be handled with special care to ensure that the integrity of the blind is maintained and the potential for bias is minimized. This can include making special provisions, such as segregating the data in question from view by the investigators, clinical team, or others as appropriate until the time of database lock and unblinding.

Each phase of the study will be unblinded after DSMB review of safety data collected through Day 56. Some key personnel of the sponsor, not involved in study operations, may be unblinded at the time of Study Steering Committee analysis. The investigator may in an emergency determine the identity of the intervention by contacting the IWRS. While the responsibility to break the intervention code in emergency situations resides solely with the investigator, it is recommended that the investigator contact the sponsor or its designee if possible, to discuss the particular situation, before breaking the blind.

Telephone contact with the sponsor or its designee will be available 24 hours per day, 7 days per week. In the event the blind is broken, the sponsor must be informed as soon as possible. The date, time, and reason for the unblinding must be documented in the IWRS and in the source document. The documentation received from the IWRS indicating the code break must be retained with the participant's source documents in a secure manner.

Participants who have had their intervention assignment unblinded should continue to return for scheduled evaluations. Participants should not be allowed to receive further study vaccinations and are only to be followed for safety evaluation visits.

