4.4 Full Analysis Set (FAS)

The FAS will include all participants in the AEC who received at least one dose of the study vaccine and provided at least one evaluable immunogenicity sample both at baseline and after baseline.

Subjects who received a treatment other than that to which they were randomized, but for whom the treatment received can be unequivocally confirmed, will be analyzed as treated, provided they have no other deviations that compromise their data.

Immunogenicity data will be censored (excluded) from immunogenicity analyses at all-time points following the first date of (1) administration of a non-study (licensed) COVID-19 vaccine OR (2) positive SARS-CoV-2 test OR (3) onset of COVID-19 illness

All Immunogenicity analyses will be based on FAS and PPS.

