5.4 Handling of Missing or Incomplete Dates

Unless otherwise specified, missing data will not be imputed for the analyses.

Medications with partial or missing dates will be imputed as follows:

- **Missing or partial medication start date:**
 - If only DAY is missing, the first day of the month will be assumed.
 - If DAY and Month are both missing, the first day of the year will be assumed.
 - If DAY, Month and Year are all missing, the date before the first dose date (Day 1) will be assumed.
- **Missing or partial medication stop date:**
 - If only DAY is missing, the last day of the month will be assumed.
 - If DAY and Month are both missing, the last day of the year will be assumed.

-
- c. If DAY, Month and year are all missing, 'ongoing' status to stop date will be assigned.

AEs with missing or incomplete onset dates will be counted as treatment emergent unless the event has a complete end date that occurs prior to the first vaccination dose OR month and year of AE onset or stop date indicate the AE occurs prior to the first vaccination dose.

Imputation rules for missing or partial AE start date are defined below:

If only day of AE start date is missing:

- If the AE start year and month are the same as that for the first dose date, and if the full (or partial) AE end date is not before the first dose date or AE end date is missing, then impute the AE start day as the day of first dose date;
- Otherwise, impute the AE start day as 15 of the month and compare with the AE end date if not missing. If the AE end date is before the imputed AE start date, set AE start date to AE end date.

If Day and Month of AE start date are missing:

- If AE start year = first dose year, and if the full (or partial) AE end date is not before the first dose date or AE end date is missing, then impute the AE start month and day as the month and day of first dose date;
- Otherwise, impute the AE start month as July and the day as 1 and compare with the AE end date if not missing. If the AE end date is before the imputed AE start date, set AE start date to AE end date.

There will be no imputation for completely missing or partial AE end dates. If the start date is completely missing for an AE, the AE is considered to be treatment-emergent unless the collection date is prior to the treatment start date.

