6.4 Immunogenicity Analyses

Unblinded Immunogenicity analyses will be provided at day 35 and day 56 analyses

Immunogenicity analysis will censor the immunogenicity measurements first time after the participants receive a licensed (non-study) COVID-19 vaccines or tested positive SARS-CoV-2 infection or develop COVID-19 illness during the study

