6.4.2 Analysis of Immunogenicity Endpoints

The immunogenicity endpoints are defined in Section 2.

- GMT and the geometric mean fold increase (GMFR) in serum antibody titer post-vaccination over Day 1 (baseline) at Days 7, 28, 35, 56, 112, 224 and 336 (Phase 1a, groups G1, G2 and G3); at Days 7, 14, 28, 56, 84, 168 and 336 (Phase 1b groups G4 and G5);
 - Neutralizing activity against multiple variant spike protein-expressing pseudovirus, and/or PRNT₉₀ neutralizing activity against wild-type SARS-CoV-2 virus and the variant Beta (B1.351) in all participants.
 - RBD Antibody titers against wild-type variant spike protein measured by ELISA.

Confidence intervals for the difference of geometric means will be included for the pairwise comparison of treatment groups.

The 95% CI for GMTs will be obtained within each group separately. The 95% CI for the mean of log-transformed titer/concentration will be first obtained assuming that log-transformed concentrations/titers are normally distributed with an unknown variance. The 95% CI for GMTs will be then obtained by exponential-transformation of the 95% CI for the mean of log-transformed titers using analysis of variance (ANOVA) model.

SAS® Code for comparing GMTs:

```
PROC MIXED DATA=<Data>; * specify and sub-select data set as applicable;
```

```
*BY Agegrp; * as applicable;
```

```
CLASS trtpn; * other factors may be added, if applicable;
```

```
MODEL AVAL = trtpn; * AVAL=10**titer
```

```
* add factors and options (e.g. ALPHA=.. Solutions) as applicable;
```

```
LSMEANS trtpn / CL ALPHA=0.05 STDERR; * modify/adapt as applicable
```

```
Ods output LSMEANS =_outmix;
```

```
RUN;
```

```
QUIT;
```

```
Data _outmix;
```

```
Set _outmix;
```

GMT= 10**(Estimate);

GMT_LCL = 10**(Lower);

GMT_UCL = 10**(Upper);

RUN;

The GMFR will be derived by using Analysis of Covariance (ANCOVA) to model the difference in the log of the titer values between post vaccination (Day 56) and baseline (Day 0), with treatment group as main effect and baseline titer as covariate. The GMFR will be compared between the treatment groups. Pair-wise comparisons between the treatments groups will be performed using two-sided, 95% confidence, based on the least-squares mean differences from the ANCOVA model.

SAS® Code for comparing GMFR:

```
PROC MIXED DATA=<Data> (analysis dataset);  
class trtpn;  
model diff= trtpn Base; * diff = log10Day56 – log10Day0. Base=log10Day0  
Lsmeans trtpn/cl alpha=0.05;  

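### After Day 56 the only GMT comparison of G4 with G5 that the SAP specifies ignores baseline and earlier titers in a censored sample; it is less precise than it need be, and may be biased if censoring depends on titer

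*SAP*

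**What the plan says.** - **Censoring.** SAP 6.4 states: "Immunogenicity analysis will censor the immunogenicity measurements first time after the participants receive a licensed (non-study) COVID-19 vaccines". SAP 4.4 (FAS) sets out the rule in full, "Immunogenicity data will be censored (excluded) from immunogenicity analyses at all-time points following the first date of" a licensed vaccine, a positive SARS-CoV-2 test or the onset of illness. SAP 4.5 repeats it for the PPC. Both immunogenicity sets lose the same titers, so comparing FAS with PPC does not test the rule.
- **Missing data.** SAP 5.4: "Unless otherwise specified, missing data will not be imputed for the analyses".
- **Models.** The GMT code in SAP 6.4.2 is "MODEL AVAL = trtpn". It has no visit, subject, repeated or baseline term. The fold-rise (GMFR) ANCOVA does adjust for baseline titer, but both its text and its code are written for the Day 56 change only. Pairwise intervals between groups are planned, and the endpoints run to Day 336.
- **Unblinding.** Protocol 8.7.1: "Each phase of the study will be unblinded after DSMB review of safety data collected through Day 56". Protocol 7.15 restricts other vaccines only within 28 days of a study dose.
- **Purpose of G5.** The Version 5.0 amendment rationale says that G5 was raised from 9 to 27 "to better characterize the kinetics of the longer-term antibody response post-mRNA vaccination and the comparisons with the active group". Protocol 10.1.2 singles out Day 168 for Phase 1b.
- **Sample size.** SAP 3.3 allows for about 10% drop-out and states no allowance for censoring.

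**The concern.** A treatment-only comparison of whoever is still uncensored at a visit is unbiased only if, within each arm, being censored is unrelated to titer at that visit. The SAP neither states nor examines this condition. One censoring event is infection, whose independence of neutralizing titer would be a bold assumption in a vaccine trial. Once arms are known, uptake of a licensed vaccine may also differ by arm.

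Earlier titers, which help to predict the missing ones, do not enter the comparison. At stake is the long-term G4 v G5 contrast, which was part of the reason for enlarging G5: its interval may be wider than necessary and its point estimate shifted.

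**Working it through.** **1. The plan's own figure.** Drop-out: 54 × 0.9 = 48.6, which agrees with the stated 48 completers (24 per arm). The 80% power for a two-fold difference comes without an SD, so it can only be solved backwards. With two-sided alpha 0.05 and a normal approximation, SD = log10(2) × √(n/2) / (1.960 + 0.842):
- n = 24: 0.301 × 3.464 / 2.802 = 0.372
- n = 27: 0.301 × 3.674 / 2.802 = 0.395

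**2. Precision lost to censoring.** The 95% interval for the ratio is the estimate multiplied and divided by 10^(t × SD × √(1/n4 + 1/n5)). The retained numbers are assumptions.

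| Retained G4/G5 | Factor (power), SD 0.372 | Factor (power), SD 0.50 |
|---|---|---|
| 24/24 | 1.64 (80%) | 1.95 (55%) |
| 20/16 | 1.79 (68%) | 2.19 (43%) |
| 16/8 | 2.16 (46%) | 2.81 (28%) |

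**3. When bias arises.** On the log10 scale, the bias of the by-visit contrast is [mean of uncensored G4 − mean of all G4] − [the same for G5]. If censoring depends on arm alone, both brackets are zero. If low titers are censored more, both are positive, and the sign of the difference depends on which arm is selected harder.

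**4. Size at Day 168, first simulation.** Assumptions: log10 SD 0.4, AR(1) correlation 0.85, monotone censoring after Day 56 driven by the last observed titer, true ratio 2.00.

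| Censoring depends on | Retained G4/G5 | Treatment-only ratio | Fraction of truth | Repeated measures |
|---|---|---|---|---|
| Arm only | 78%/45% | 2.00 | 1.00 | 2.01 |
| Titer, mild | 71%/61% | 1.91 | 0.96 | 2.00 |
| Titer, strong | 75%/57% | 1.77 | 0.89 | 2.00 |
| Arm + titer, mild | 83%/43% | 1.68 | 0.84 | 1.99 |
| Arm + titer, strong | 85%/41% | 1.47 | 0.74 | 2.00 |
| Titer strong, G4 censored more | 62%/70% | 2.11 | 1.06 | 2.00 |

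At 27 per arm, coverage of the treatment-only 95% interval was 95% (arm only), 92% (arm + mild titer) and 86% (arm + strong titer).

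**5. Other assumptions.** A second simulation (between-person SD 0.40, within-person SD 0.20; 65-75% of G4 and 47-51% of G5 retained) gave 1.00, 0.85 and 0.76 of the truth with no, moderate and strong titer dependence. With equal vaccine uptake in both arms and moderate dependence it gave 0.92. Using earlier titers gave 1.00. A third, at 27 per arm, gave 0.99, 0.85 and 0.76 for the treatment-only model, 0.93-1.00 for a single-visit baseline ANCOVA, and 1.00 using all earlier titers.

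**6. Precision recovered.** In the first simulation the SD of the log10 ratio fell from 0.138-0.147 to 0.124, so variance fell by 1 − (0.124/0.138)² = 19% to 1 − (0.124/0.147)² = 29%. In the second, variance fell by 20-30% with no or moderate dependence and not at all with strong dependence. In the third, the SD fell from 0.16-0.17 to 0.10-0.11, or roughly 60% less variance (1 − (0.10/0.16)² = 61%; 1 − (0.11/0.17)² = 58%).

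**7. If censoring depends on the unobserved current titer.** With more censoring in G5, treatment-only gave 1.62 (mild) to 1.36 (strong) against 2.00, and repeated measures 1.88 to 1.75. The model reduces this bias but does not remove it.

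**The case against.** The strongest reply is that the documents do not show bias. A reader might infer that the contrast is biased because participants are unblinded, that the remaining placebo participants are a high-titer subset, and that durability is therefore understated. The documents support none of this as fact. They give no censoring rates, do not say that censoring depends on arm or titer, do not offer placebo recipients a licensed vaccine, and do not say when each participant learns the allocation. Arm-dependent censoring alone leaves the ratio unbiased, and the direction can reverse. All of this stands.

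Nor does the high-titer-subset reading carry over to Phase 1a. G3 enters unvaccinated and with no diagnosed infection, and its titers after either event are removed. What remains is essentially naive, with little titer variation to select on.

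The SAP also already has a baseline-adjusted ANCOVA, and baseline adjustment supplies most of the gain. That stands too, but the ANCOVA is written for Day 56 only. Comments in the code allow factors to be added and the data to be sub-selected, so separate by-visit fits are an inference. Even so, no other post-Day 56 comparison model is given.

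Finally, Protocol 4.13 calls the immunogenicity results descriptive, and 10.3 calls them exploratory. The stated development criteria rest on Days 28 and 56, the convalescent panel and the post-boost fold rise. No stated decision uses the later contrast. This limits the weight of the point without answering it.

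**Conclusion.** The gap is real and narrow. After Day 56 the specified GMT comparison is unadjusted and made on a censored sample, and no adjusted model is given. In most scenarios examined, the Phase 1b contrast at Days 84, 168 and 336 is less precise than the collected data allow; the gain from using earlier titers ranged from none to about 60% of the variance.

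Bias is possible, not established. It requires censoring to depend on titer or on something that predicts titer. Under assumed moderate to strong dependence, with G5 censored at least as much as G4, the estimated ratio is about 0.75 to 0.92 of the truth. These figures rest on assumed SDs, visit correlations and censoring rates. The rule applies from Day 1, but the exposure is mainly after Day 56, when follow-up is long and the arms are unblinded. This is a worthwhile improvement to a secondary, descriptive contrast, not a threat to the trial's main conclusions.

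**What to change.** In SAP 6.4.2:
- Make the between-group comparison at post-baseline visits a repeated-measures PROC MIXED on log10 titer from all uncensored visits, with treatment × visit and baseline × visit, unstructured covariance and Kenward-Roger degrees of freedom. Phase 1b has seven post-baseline visits, hence 7 × 8 / 2 = 28 covariance parameters, so name a fallback that allows unequal variances and spacing, such as heterogeneous Toeplitz or spatial power. Fit the phases separately; in Phase 1a, check that a pooled covariance suits a placebo arm near the assay floor.
- At minimum, extend the existing baseline ANCOVA to every visit after Day 56.
- State that the estimates refer to the course without other vaccine or infection.
- Report numbers and reasons censored by arm and visit, and keep the by-visit GMTs as description.
- Add a simple delta sensitivity analysis for censoring that depends on unobserved titer.

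The cost is SAP wording and one model in a procedure already used, with no new data. The downside is that the model relies on censoring being explained by arm and earlier titers; hence the delta analysis.

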6.4.1 Immunogenicity Evaluations

Immunogenicity will be assessed by measuring serum nAB titers against wild-type SARS-CoV-2 virus (PRNT) and/or spike protein-expressing pseudovirus (microneutralization), serum binding antibody titers against spike protein and the spike protein receptor-binding domain (RBD), and peripheral blood mononuclear cell (PBMC) T cell responses against spike protein.

Testing will include assessment of responses against spike protein of the original SARS-CoV-2 isolate as well as spike protein of variant Beta (B.1.315) and other variants. In Phase 1a, time points for evaluation will be at Study Days 1, 7, 28, 35, 56, 112, 224 and 336. In Phase 1b, time points for evaluation for groups G4 and G5 will be at Study Days 1, 7, 14, 28, 56, 84, 168 and 336.

Neutralizing antibody and binding antibody results will be presented as the geometric mean titer (GMT) and the geometric mean fold increase in titer post-vaccination over baseline. T cell responses will be presented as the geometric mean number of IFN-ELISPOT-positive cells per 10^6 PBMCs.

Geometric mean nAb titers and antibodies to the receptor binding domain (RBD) for 5 µg and 10 µg dose groups at Day 1, 7, 28, 35 and 56 will be compared to each other and pooled COVID-19 convalescent serum to select the optimal dose of VBI-2902a in the age cohorts.

6.4.2 Analysis of Immunogenicity Endpoints

The immunogenicity endpoints are defined in Section 2.

- GMT and the geometric mean fold increase (GMFR) in serum antibody titer post-vaccination over Day 1 (baseline) at Days 7, 28, 35, 56, 112, 224 and 336 (Phase 1a, groups G1, G2 and G3); at Days 7, 14, 28, 56, 84, 168 and 336 (Phase 1b groups G4 and G5);
 - Neutralizing activity against multiple variant spike protein-expressing pseudovirus, and/or PRNT₉₀ neutralizing activity against wild-type SARS-CoV-2 virus and the variant Beta (B1.351) in all participants.
 - RBD Antibody titers against wild-type variant spike protein measured by ELISA.

Confidence intervals for the difference of geometric means will be included for the pairwise comparison of treatment groups.

The 95% CI for GMTs will be obtained within each group separately. The 95% CI for the mean of log-transformed titer/concentration will be first obtained assuming that log-transformed concentrations/titers are normally distributed with an unknown variance. The 95% CI for GMTs will be then obtained by exponential-transformation of the 95% CI for the mean of log-transformed titers using analysis of variance (ANOVA) model.

SAS® Code for comparing GMTs:

```
PROC MIXED DATA=<Data>; * specify and sub-select data set as applicable;
```

```
*BY Agegrp; * as applicable;
```

```
CLASS trtpn; * other factors may be added, if applicable;
```

```
MODEL AVAL = trtpn; * AVAL=10**titer
```

```
* add factors and options (e.g. ALPHA=.. Solutions) as applicable;
```

```
LSMEANS trtpn / CL ALPHA=0.05 STDERR; * modify/adapt as applicable
```

```
Ods output LSMEANS =_outmix;
```

```
RUN;
```

```
QUIT;
```

```
Data _outmix;
```

```
Set _outmix;
```

GMT= 10**(Estimate);

GMT_LCL = 10**(Lower);

GMT_UCL = 10**(Upper);

RUN;

The GMFR will be derived by using Analysis of Covariance (ANCOVA) to model the difference in the log of the titer values between post vaccination (Day 56) and baseline (Day 0), with treatment group as main effect and baseline titer as covariate. The GMFR will be compared between the treatment groups. Pair-wise comparisons between the treatments groups will be performed using two-sided, 95% confidence, based on the least-squares mean differences from the ANCOVA model.

SAS® Code for comparing GMFR:

```
PROC MIXED DATA=<Data> (analysis dataset);  
class trtpn;  
model diff= trtpn Base; * diff = log10Day56 – log10Day0. Base=log10Day0  
Lsmeans trtpn/cl alpha=0.05;  
Ods output LSMEANS =_outmix;  
run;  
Quit;  
Data _outmix;  
Set _outmix;  
GMFR = 10**(Estimate);  
GMFR_LCL = 10**(Lower);  
GMFR_UCL = 10**(Upper);  
Run;
```

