Geometric mean titers (GMT) of nAb and binding antibodies to the spike protein and its receptor binding domain (RBD) in one-dose and two-dose groups in Phase 1a at Days 1, 7, 28, 35 and 56 will be compared against a panel of COVID-19 convalescent sera as well as a WHO International Standard of high titer pooled COVID-19 convalescent sera. Day 28 antibodies to RBD and T-cell endpoints will be considered if Day 56 nAb results do not allow a clear determination of equivalence or superiority. If responses are inferior to that of the panel of convalescent serum in Phase 1a and Phase 1b, neither VBI-2902a nor VBI-2905a will undergo further testing at the proposed dose levels and dose regimens. In Phase 1b, the percentage of subjects with a 4-fold or greater increase in nAb titers will be determined, as this represents a meaningful boosting of immunity.

The group sizes will allow determination of at least two-fold differences in nAb titers at a power of 80% with an alpha error of 0.05. Safety and tolerability will be evaluated in the total of ~67 participants who will receive at least one dose of VBI-2902a or VBI-2905a and in ~47 participants who will receive placebo. If no safety signals are detected and immunogenicity is demonstrated, further clinical development will be considered. Further clinical development may not be considered if optimal nAb titers are not equivalent to or superior to that of the panel of COVID- 19 convalescent serum. The safety, tolerability and percentage of subjects with 4-fold or greater increases in nAb titers at Days 28 and 56 will be used to determine whether further clinical development of a one-dose vaccination regimen is justified.

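### SAP 6.4.2 promises confidence intervals for a difference of geometric means, but its log-scale model gives ratios and the printed code requests no between-group contrast

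*SAP*

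**What the plan says.** All of the relevant analysis text is in SAP 6.4.2 (Analysis of Immunogenicity Endpoints).

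- **Promised comparison of GMTs:** "Confidence intervals for the difference of geometric means will be included for the pairwise comparison of treatment groups".
- **Method for GMTs:** "The 95% CI for GMTs will be obtained within each group separately". The interval comes from "exponential-transformation of the 95% CI for the mean of log-transformed titers using analysis of variance (ANOVA) model".
- **GMT code:** the block is headed as code for comparing GMTs. Its key statement is "LSMEANS trtpn / CL ALPHA=0.05 STDERR". It saves the LSMEANS table only and applies `10**` to each group's estimate and limits. The comment on the MODEL statement sets AVAL to `10**titer`.
- **Method for GMFR:** an ANCOVA on the change in log titer with baseline as covariate. The prose calls for pairwise, two-sided 95% comparisons from least-squares mean differences.
- **GMFR code:** the block is headed as code for comparing GMFR. Its LSMEANS statement asks for confidence limits at alpha 0.05 and nothing else. It too saves only the LSMEANS table and back-transforms only group values.

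The protocol states the effect of interest in folds. Section 4.4 says: "The group sizes will allow determination of at least two-fold differences in nAb titers". Section 4.13 says that the VBI-2905a booster in G4 will be assessed by comparison with G5. Section 10.3 calls the immunogenicity results exploratory and reports no formal power calculation.

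**The concern.** Three things in one section do not fit together.

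1. The quantity named (a difference of geometric means) is not the quantity that the described model estimates (a ratio), and no method is given for an interval on the difference.
2. The code offered for comparing groups contains no comparison.
3. The comment that defines the response variable inverts the transform on which the whole section depends.

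The between-group estimate matters most for G4 v G5, the randomized comparison that Protocol 4.13 relies on to assess the booster. SAP 6.4 schedules unblinded immunogenicity analyses at Days 35 and 56, so the comparative estimate should be fixed before anyone sees data. As written, one programmer could deliver group GMTs only, another a difference in titer units, and another a ratio. Each could claim to follow the SAP.

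**Working it through.** **The plan's own figure.** The only related number is 80% power for a two-fold difference at alpha 0.05 (Protocol 4.4; SAP 3.3). It cannot be reproduced, because no SD is given. Two-fold is log10(2) = 0.301 on the log scale. With a two-sided alpha, the largest SD that gives 80% power is 0.301 / [√(2/n) × (1.960 + 0.842)]:

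- n = 20 per arm: 0.301 / (0.3162 × 2.802) = 0.340 log10
- n = 27 per arm: 0.301 / (0.2722 × 2.802) = 0.395 log10

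The point does not rest on this figure. What matters is that the effect is a ratio. The SD of 0.34 is carried into the illustration below as an assumption.

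**Ratio or difference.** Let m1 and m2 be the mean log10 titers, so each GMT is 10^m. Then 10^(m1 − m2) = GMT1 / GMT2. A back-transformed contrast is therefore a ratio. Illustration with assumed n = 20 per arm, SD 0.34 log10 and 38 df (t = 2.024):

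- SE of the contrast = 0.34 × √(2/20) = 0.1075, and t × SE = 0.218.
- Ratio CI for a two-fold effect: 10^(0.301 ± 0.218) = 1.21 to 3.30.
- For the difference, a delta-method SE is ln(10) × √[(GMT1 × s)² + (GMT2 × s)²], with s = 0.34/√20 = 0.0760.

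| GMTs | Ratio (95% CI) | Difference (95% CI) |
|---|---|---|
| 200 v 100 | 2.00 (1.21 to 3.30) | 100 (20.8 to 179.2) |
| 2000 v 1000 | 2.00 (1.21 to 3.30) | 1000 (208 to 1792) |

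The same two-fold effect gives one answer on the ratio scale and two on the difference scale.

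**What the GMFR contrast estimates.** The response is log post-titer minus log baseline, and log baseline is also a covariate. The group coefficient is therefore the same as in a model for log post-titer. In a simulated data set with 24 per arm it was 0.2888 both ways. Back-transformed, 10^0.2888 = 1.94 (95% CI 1.37 to 2.76), which is a ratio of GMFRs.

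**What the code produces.**

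| Step | GMT block | GMFR block |
|---|---|---|
| DIFF/PDIFF, ESTIMATE or CONTRAST | none | none |
| Table saved | LSMEANS | LSMEANS |
| Back-transformed | group mean and limits | group mean and limits |
| Prose calls for a pairwise comparison | yes, as a difference of geometric means | yes, from LS-mean differences |

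**Can the contrast be recovered from the group output?** For GMT, yes: in a one-way ANOVA the SE of the contrast is √(SE1² + SE2²). For GMFR, not exactly, because adjusted means share the covariate. In the simulation √(0.05298² + 0.05298²) = 0.0749, against a true SE of 0.0758.

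**The AVAL comment.** Back-transforming by `10**` returns a GMT only if AVAL is log10(titer). The GMFR block's comments do use log10. Read literally, `10**titer` is the inverse: a titer of 100 becomes 10^100, and a titer of 400 overflows double precision.

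**The case against.** The strongest defence is that the code is illustrative. The GMT block says so: "LSMEANS trtpn / CL ALPHA=0.05 STDERR; * modify/adapt as applicable". A competent programmer would add the missing option, and the sentence on pairwise intervals obliges them to. For GMFR the prose already defines the right contrast. Table templates are in a separate document (SAP 1). A reader might infer that the comparison will never be produced; the documents do not support that. What they show is that the code as printed does not produce it. The defence is weaker for GMT than it looks, because no text there defines a ratio, so adapting the code to the prose means aiming at the wrong quantity. The GMFR block carries no comment inviting adaptation.

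It is also fair to say that 'difference' may be loose wording. The protocol and SAP themselves speak of a two-fold difference, and nothing in the SAP sets out a CI in titer units. That may well be the intent, but the SAP never names a ratio of GMTs.

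Two further inferences are tempting and not supported:

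- **That arms will be judged by whether separate group intervals overlap.** No section states such a rule, so the power lost under one is not a property of this plan.
- **That the four-fold benchmark is undermined.** Protocol 4.13 states it as a rise in titer after the boost, and 4.4 as a percentage of subjects with such a rise. Neither is a ratio between arms, and the GMFR block does give each group's fold rise with limits. The Phase 1a criterion compares vaccine titers with convalescent sera, which a contrast among randomized arms would not supply.

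**Conclusion.** The point holds as an internal error in SAP 6.4.2. The named quantity does not match the model, the printed code for comparing groups contains no comparison, and the AVAL comment reverses the required transform. The gap is widest for GMT, where neither text nor code defines the right contrast. For GMFR the prose is adequate and the code fails to follow it.

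The impact is modest. Immunogenicity is secondary and exploratory, no numeric between-arm threshold is set for G4 v G5, and no data are lost. What is missing is a clear prespecified estimate for the comparison that Protocol 4.13 calls for. That a log-scale contrast back-transforms to a ratio, and what the code omits, need no assumption. The intervals shown rest on the assumed 20 per arm and SD of 0.34 log10, and the GMFR figures on simulated data.

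**What to change.** In SAP 6.4.2:

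1. Replace the sentence on the difference of geometric means with: *Ratios of GMTs (and ratios of GMFRs) with two-sided 95% CIs will be presented for each pairwise comparison of treatment groups.* State which group is the numerator.
2. Correct the comment in the GMT block to `AVAL=log10(titer)`.
3. In both blocks use `LSMEANS trtpn / DIFF CL ALPHA=0.05`.
4. Save both the LSMEANS and the DIFFS tables, and back-transform Estimate, Lower and Upper from each as `10**x`. The first gives group GMTs or GMFRs, the second their ratios.

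The cost is one sentence, one comment, one option in each of two statements, and one extra output table and back-transformation step per block. Data collection, sample size and the models are unchanged. Adding DIFF without correcting the AVAL comment would leave the GMT block wrong if it is read literally, so the changes should be made together.
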